3. SUBJECT POPULATIONS

3.1. Analyses Sets Definitions

The following data sets will be used for reporting of safety data from the trial:

Safety Analysis Set (SAF): All randomized subjects who received at least one dose of double-blind study drug irrespective of the treatment received. Subjects will be analyzed according to treatment received.

Follow-up Safety Set (FU SAF): All randomized subjects who entered the drug free follow-up period. Subjects will be analyzed according to treatment received.

Subjects who entered the drug free follow-up period are :

- subjects eligible to the 6 months treatment free follow-up (subject who completed the six months of treatment or discontinued the study treatment between Month 3 and Month 6), and
- with any data post month 6 or post treatment discontinuation assigned to a follow-up visit.

The actual treatment will be derived as follows, based on daily e-diary IMP intake data:

Subjects received a different kit of active linzagolix or placebo for each month, and a different kit for add-back or placebo for each 3-month period.

The number of days with one pink tablet, one grey tablet and one red capsule taken based on e-diary IMP intake data for each treatment will be computed. Data from "Today" will be used primarily. If data from today is missing, data from "Yesterday" of the following day will be considered. If the e-diary is not completed for a day (neither "Today" nor "Yesterday" of following day), it will be assumed that no drug was taken on that day.

Further rules are as follows:

- Treatment administration errors:
 - If a subject received placebo with placebo ABT in more than 50% of days, then the actual treatment group will be placebo with placebo ABT.
 - Otherwise, the active treatment group (combined with add-back or placebo add-back) with the most days taken will be assigned.
 - If the number of days is equal for two treatments groups containing active treatment then LGX 200 mg with ABT will be assigned.
- If a subject discontinued, only data received up to discontinuation will be used.
- It is possible that the derived actual treatment group does not correspond to any of the planned treatment groups. In that case actual treatment group will be assigned to the planned treatment group with same dose of active treatment. Example: LGX 75mg with ABT

Sponsor:	ObsEva		
Protocol:	18-OBE2109-002		
Document Version No.:	1.0	Document Date:	18-MAY-2021

will be assigned to LGX 75mg with placebo ABT ; LGX 200mg with placebo ABT will be assigned to LGX 200mg with ABT. A listing with such cases will be provided.

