4.2.7. Withdrawals, Dropouts, Loss to Follow-up

In general, there will be no substitutions made to accommodate missing data points due to withdrawals, dropouts and loss to follow-up. All data recorded in the CRF will be included in data listings that will accompany the clinical study report.

In case of early discontinuation, the subject was to be instructed to complete the relevant eDiary questionnaires as soon as possible upon treatment discontinuation.

Subjects who did not receive the study drug will be withdrawn from the study and no further study procedures will be performed.

Sponsor:	ObsEva		
Protocol:	18-OBE2109-002		
Document Version No.:	1.0	Document Date:	18-MAY-2021

Withdrawal during treatment period:

Subjects who discontinue between Day 1 and Month 3 should undergo the procedures required at Month 6 (except the DXA scan and the endometrium biopsy if a biopsy was obtained at screening) and will not enter the 6-month follow-up period.

Subjects discontinuing the study treatment between Month 3 and Month 6 should undergo the procedures required at Month 6. These subjects will enter a 6-month follow-up period and will continue daily eDiary recording for 6 months and up to Month 6 FU visit in order to continue to collect efficacy data.

PK sampling is not required if the subject had no IMP administration the day prior to the withdrawal visit.

Withdrawal during follow-up period:

Subjects discontinuing participation in the study during the follow-up period should undergo the procedures required at Month 6 FU visit, which includes completion of all ClinRO and ePRO questionnaires, except the DXA in case of discontinuation before Month 3 FU visit.

Subject Replacement:

Discontinued subjects who did not receive the study drug may be replaced.

Additional subjects may be recruited due to subjects who were discontinued due to ALT, AST, GGT or total bilirubin \geq 2 times the upper limit of normal at Day 1, or due to a clinically significant biopsy finding at Day 1 (treatment start), or due to high calcium level at Day 1.

4.2.8. Missing, Unused, and Spurious Data**4.2.8.1. Adverse events and Concomitant Medication Missing Dates**

Imputation of missing/partial AE and CM dates will be done only to identify treatment-emergent AEs.

AE onset dates:

- Partially missing AE onset dates will be imputed as follows:
 - o When only Day is missing:

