For other safety results, data from early discontinuation should be compared to theoretical visits dates. Only assessments within the window of theoretical date +/-14 days will be used for analyses, if it is planned to have a such assessment at this visit and no other assessment is in the window. If a subject discontinued in the main treatment period, date will be compared to the theoretical visit dates in main treatment period as described in Table 3. If a subject discontinued in the follow-up period, date will be compared to the theoretical visit dates in Follow-up period from

Sponsor:	ObsEva		
Protocol:	18-OBE2109-002		
Document Version No.:	1.0	Document Date:	18-MAY-2021

Table 4.

For unscheduled safety assessments, if the assessment occurs in a window of +/- 14 days of a planned eCRF visit for which it was planned per protocol to have such assessment, and no assessment was done for that visit, the assessment will be assigned to that visit. If the assessment is equally distant from two eCRF visits with no corresponding safety assessment, the assessment will be assigned to the next visit.

For biopsy, DXA assessment or laboratory assessment, if an assessment has been assigned in external data to a follow-up visit of the main study for subjects entered extension study, the visit of assessment should be reassigned with the same rules described above for unscheduled safety assessment.

Table 3 Theoretical Visit Dates in Main Treatment Period

Visit	Theoretical Date
Month 1	Day 29
Month 2	Day 57
Month 3	Day 85
Month 4	Day 113
Month 5	Day 141
Month 6	Day 169

Sponsor:	ObsEva		
Protocol:	18-OBE2109-002		
Document Version No.:	1.0	Document Date:	18-MAY-2021

Table 4 Theoretical Visit Dates in Follow-up

Visit	Theoretical Date
Month 1 FU	Month 6 date or treatment discontinuation date + 28
Month 2 FU	Month 6 date or treatment discontinuation date + 56
Month 3 FU	Month 6 date or treatment discontinuation date + 84
Month 4 FU	Month 6 date or treatment discontinuation date + 112
Month 5 FU	Month 6 date or treatment discontinuation date + 140
Month 6 FU	Month 6 date or treatment discontinuation date + 168

4.2.11. **Baseline Definition**

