4.2.12. Last treatment administration date, End of Study date and Period definitions

The last treatment administration date will be defined as the date of treatment termination recorded in the main period eCRF page. If this date is missing, the last date with a drug intake in eDiary prior to the Month 6 date or, for subjects who discontinued, the last date with available drug intake information in the subject eDiary will be used.

The end of study date will be the last assessment date in the main study defined as last eCRF or ediary date prior to and not including Month 6 for subjects who entered the Extension, and the last eCRF or ediary date in the main study or main follow-up if not. This will not necessarily be the same date as last assessment date as recorded in the eCRF.

Note: For summaries by visit (efficacy or safety), the Month 6 assessments will be included in the main study analyses. For Adverse Events, Concomitant Medications and Daily diaries, data collected on Month 6 date will be part of the extension for subjects entering the extension study and be part of the Follow-up period for subjects entering the main study follow-up period.

The main treatment period will be defined as Day 1 up to (Month 6 date -1) or the treatment discontinuation date.

The main follow-up period will be defined as the Month 6 date or (treatment discontinuation date+1) up to the end of study date (for subjects who entered into the main follow-up period).

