7.2. Appendix B: Statistical Tables/Figures/Listings to be Generated

Section 14.1 Demographic Data and Subject Characteristics

- Table 14.1.1 Patients Screened and Randomized by Country and Site - Screened Set
- Table 14.1.2.1 Patient Disposition by treatment group – Randomized Subjects
- Table 14.1.2.2 Patient Disposition by treatment group – Safety Analysis Set
- Table 14.1.3 Analysis Sets – Randomized Set
- Table 14.1.4 Number of Subjects by Visit – Safety Set
- Table 14.1.4 Major Protocol Deviations - Safety Set
- Table 14.1.5 Demographic and Baseline Characteristics – Safety Analysis Set
- Table 14.1.6 Baseline Disease Characteristics: Menstrual Cycles and Pain – Safety Analysis Set
- Table 14.1.7 Baseline Disease Characteristics: Transvaginal Ultrasound – Safety Analysis Set
- Table 14.1.8 Other Baseline examinations - Safety Analysis Set
- Table 14.1.9 Medical History - Safety Analysis Set
- Table 14.1.10 Endometriosis History – Safety Analysis Set
- Table 14.1.11.1 Exposure and Compliance to Study Treatment from Day 1 to Month 6 - Safety Analysis Set

Section 14.3.1 Adverse Events

- Table 14.3.1.1.1 Summary of Treatment-Emergent Adverse Events from Day 1 to Month 6 - Safety Analysis Set
- Table 14.3.1.1.2 Summary of Treatment-Emergent Adverse Events from Month 6 to Month 6 FU - Follow-up Safety Analysis Set
- Table 14.3.1.2.1 Treatment-Emergent Adverse Events by MedDRA SOC and Preferred Term from Day 1 to Month 6 - Safety Analysis Set
- Table 14.3.1.2.2 Treatment-Emergent Adverse Events by MedDRA SOC and Preferred Term from Month 6 to Month 6 FU – Follow-up Safety Analysis Set
- Table 14.3.1.3.1 Treatment-Emergent Adverse Events by Maximum Severity by MedDRA SOC and Preferred Term from Day 1 to Month 6 - Safety Analysis Set

Sponsor:	ObsEva		
Protocol:	18-OBE2109-002		
Document Version No.:	1.0	Document Date:	18-MAY-2021

- Table 14.3.1.3.2 Treatment-Emergent Adverse Events by Maximum Severity by MedDRA SOC and Preferred Term from Month 6 to Month 6 FU - Follow-up Safety Analysis Set
- Table 14.3.1.4.1 Treatment-Emergent Adverse Events Related to Linzagolix by MedDRA SOC and Preferred Term from Day 1 to Month 6 - Safety Analysis Set
- Table 14.3.1.4.2 Treatment-Emergent Adverse Events Related to Linzagolix by MedDRA SOC and Preferred Term from Month 6 to Month 6 FU - Follow-up Safety Analysis Set

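### Off-drug treatment-emergent AEs in women outside both the Extension and the Follow-up Safety Set reach no summary table, although the SAP's TEAE window runs to 30 days after stopping

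*SAP*

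**What the plan says.** Four parts of the SAP bear on this.

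- **Set definition (3.1).** The Follow-up Safety Set has two conditions. The woman must be eligible for the treatment-free follow-up ("subject who completed the six months of treatment or discontinued the study treatment between Month 3 and Month 6"), and she must be someone "with any data post month 6 or post treatment discontinuation assigned to a follow-up visit".
- **Periods (4.2.12).** The main treatment period ends the day before the Month 6 date or on the discontinuation date. "The main follow-up period will be defined as the Month 6 date or (treatment discontinuation date+1) up to the end of study date", and this applies only to women who entered follow-up.
- **AE analysis (4.8.2).** TEAEs run from first dose through 30 days after stopping, and later events are classed as post-treatment AEs. AE tables are produced for the two periods of 4.2.12. Events on or after Month 6 in Extension entrants are shown only in the Extension study.
- **Table list (7.2, Appendix B).** The Day 1 to Month 6 AE tables use the Safety Analysis Set. The later ones use the narrower set, for example "Summary of Treatment-Emergent Adverse Events from Month 6 to Month 6 FU - Follow-up Safety Analysis Set".

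On visit assignment, 4.2.10 uses visits as recorded in the eCRF, except for DXA and diary questionnaires. For other safety data from early discontinuation it adds: "Only assessments within the window of theoretical date +/-14 days will be used for analyses". Section 4.2.7 expects an exit visit: "Subjects discontinuing participation in the study during the follow-up period should undergo the procedures required at Month 6 FU visit".

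**The concern.** With efficacy and PK analyses withdrawn, the safety tables are the main output of this SAP. Protocol 13.5.5 counts events up to 30 days after stopping as treatment-emergent and says that safety data are summarized on the Safety Analysis Set. The SAP keeps the 30-day window. However, it hands the off-drug part of that window to tables built on a set that some dosed women cannot enter.

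An early off-drug event, possibly serious, could then be absent from every incidence table. Protocol 12.3.2 requires sites to report SAEs they learn of up to 4 weeks after treatment discontinuation in women who left the study, so such events can reach the database without a follow-up visit. The SAP also says that the study stopped prematurely and that not all women could be followed, so missing follow-up visits are plausible.

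The same definition affects disposition (4.4). Under 3.1, an eligible woman with no datum assigned to a follow-up visit counts neither as having entered follow-up nor as having discontinued it. SAP Section 5 does not list the added data condition as a change, although the protocol's Follow-up Set (13.4) has no such condition.

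**Working it through.** The plan has no figure to reproduce here. The check is date arithmetic, followed by tracing each type of woman through the tables.

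**1. When an exit assessment maps to a follow-up visit.** Inputs are SAP Table 4 (follow-up visit k at 28k days after the Month 6 date or discontinuation date, k = 1 to 6) and the ±14-day window of 4.2.10. Days below are counted from that date.

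| Visit | Day | Mapping window (day − 14 to day + 14) |
|---|---|---|
| Month 1 FU | 28 | 14 to 42 |
| Month 2 FU | 56 | 42 to 70 |
| Month 3 FU | 84 | 70 to 98 |
| Month 4 FU | 112 | 98 to 126 |
| Month 5 FU | 140 | 126 to 154 |
| Month 6 FU | 168 | 154 to 182 |

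The windows cover days 14 to 182 without a gap. Day 13 gives |13 − 28| = 15 > 14, so it is not mapped. Day 14 gives |14 − 28| = 14, so it is mapped, provided that the assessment is planned at that visit and no other lies in the window. Days 0 to 13 map to no follow-up visit.

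**2. Which exit visits are tested against those windows.** For women leaving during follow-up: "If a subject discontinued in the follow-up period, date will be compared to the theoretical visit dates in Follow-up period from" Table 4. For women who stop on treatment: "If a subject discontinued in the main treatment period, date will be compared to the theoretical visit dates in main treatment period". The discontinuation visit of a woman stopping between Month 3 (Day 85) and Month 6 (Day 169) is therefore treatment-period data and does not by itself admit her to the Follow-up Safety Set.

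**3. Class of the event.** An AE on day 10 satisfies 10 ≤ 30, so it is a TEAE and not a post-treatment AE in the SAP's sense.

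**4. Tracing a day-10 TEAE in women who do not enter the Extension.**

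| Woman | Day 1–Month 6 table (period cut) | Month 6–Month 6 FU table (Follow-up Safety Set) |
|---|---|---|
| Completes treatment; only off-drug record is an exit assessment on or before day 13 | No, after period end | No, nothing assigned to a follow-up visit |
| Completes treatment; exit assessment on day 14 or later | No | Yes |
| Stops between Month 3 and Month 6, attends only the discontinuation visit | No | No |
| Stops before Month 3 (whatever later data exist) | No | No, ineligible |

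Three of the four have the event in no summary table. The last fails the eligibility condition, so relaxing the data condition alone would not help her.

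**5. Direction of effect on follow-up percentages.** Hypothetical arm: 20 eligible women, 2 outside the set, and 3 of the other 18 with a TEAE. The table shows 3/18 = 16.7%. With all 20 included:

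- neither of the 2 had a TEAE: 3/20 = 15%
- one had: 4/20 = 20%
- both had: 5/20 = 25%

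Exclusion removes women from numerator and denominator together, so the shift can go either way. By contrast, adding the omitted events to the Day 1–Month 6 counts on the Safety Analysis Set leaves the denominator fixed, so that percentage can only rise or stay the same.

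**The case against.** The best defence has four parts.

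- **The clause says any data.** It does not expressly bar AEs, medications or diary entries, and Appendix A (7.1) maps diary records to the main follow-up schedule. A reader might infer that such records can never qualify a woman; the documents do not go that far. Equally, they do not say that a dated record counts as assigned to a visit, and 4.2.12 allocates AEs, medications and diaries by date. The wording is ambiguous and needs settling.
- **The ±14-day rule is not a general entry rule.** It governs early-discontinuation assessments; a parallel rule covers unscheduled ones. A visit recorded in the eCRF as Month 1 FU counts on any day. This stands, and it narrows the group affected.
- **The Day 1–Month 6 tables could be run on the TEAE flag alone**, which would capture these events. That is possible, but 4.8.2 expressly ties the tables to the 4.2.12 periods. The defect is best seen as a conflict between the 30-day window and the period cut.
- **Nothing is lost from the report.** Listings of all AEs, TEAEs and serious TEAEs use the Safety Analysis Set, and AE analysis is descriptive. This stands: the gap is in the tables only.

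The SAP set is also wider than the protocol's Follow-up Set, which required six completed months of treatment.

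**Conclusion.** The gap is real and limited. Off-drug TEAEs within the SAP's own 30-day window, including serious ones, reach no summary table when the woman is outside both the Extension and the Follow-up Safety Set. This applies to women with no datum assigned to a follow-up visit and to women who stopped before Month 3.

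The conclusion rests on three readings: the 4.2.12 periods govern the AE tables, as 4.8.2 says; a date-allocated record is not by itself assigned to a visit; and the TEAE window is 30 days, as protocol 13.5.5 and the SAP's post-treatment rule both imply.

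A reader might infer more: that all women leaving in the first weeks are dropped, that post-treatment AEs vanish, and that follow-up rates are biased downward. The documents do not support this. Exit assessments from day 14 can map to Month 1 FU, the events at issue are mainly TEAEs, the listings retain them, and the direction of bias depends on the unknown event rate among the excluded women. No counts are given, so the number affected could be zero.

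**What to change.** 1. **SAP 4.2.12 and 4.8.2.** Produce the TEAE and serious TEAE tables on the Safety Analysis Set, using the TEAE flag through 30 days after last dose. Keep the existing rule that events on or after Month 6 in Extension entrants go to the Extension study. This step also covers women who stopped before Month 3.
2. **SAP 3.1.** Define the Follow-up Safety Set as women eligible for the treatment-free follow-up who did not enter the Extension and have any dated off-drug record: visit, AE, SAE, concomitant medication, eDiary entry or contact.
3. **SAP 4.4.** Count women in that set with no follow-up visit as having entered follow-up and discontinued before Month 1 FU.

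If the period-specific follow-up tables are kept beside the tables in step 1, a footnote should say that an event may appear in both.

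The cost is SAP wording and a derived flag, with no new data collection. TEAE rates may look slightly less favourable and follow-up denominators may be slightly larger.

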4.8.1.2. Compliance

Lingazolix/Placebo Grey blister (200 mg or matching placebo), Lingazolix/Placebo Pink blister (75 mg or matching placebo) and Add-back therapy compliance from the study treatment accountability page among the Day 1- End of main study treatment period will be summarized by treatment group.

If Lingazolix/Placebo and Add-back therapy compliances from accountability data are missing, compliance will be computed from daily diary data.

Compliance will be computed as the number of days with pink tablet/grey tablet/Add-back capsule taken *100 divided by the number of days in the period (Month 6 visit date/withdrawal date - Day 1). Data from “Today” will be used primarily. If data from today is missing, date from “Yesterday” will be considered. If the e-diary is not completed for a day (neither “Today” nor “Yesterday”), it will be assumed that no intake of drug was taken on that day.

Study treatment overdose and misuse will be reported in a listing.

Compliances will be reported in a listing.

Sponsor:	ObsEva		
Protocol:	18-OBE2109-002		
Document Version No.:	1.0	Document Date:	18-MAY-2021

4.8.2. **Adverse Events**

Adverse events will be coded using the Medical Dictionary for Regulatory Activities (MedDRA) and displayed in tables and listings using System/Organ/Class (SOC) and Preferred Term.

Analyses of adverse events will be performed for those events that are considered treatment emergent (TEAEs), where treatment emergent is defined as AEs with a start date on or after the first dose of study drug through 30 days after discontinuation of study drug or Month 6 visit date, or any event that was present at baseline but worsened in intensity or was subsequently considered drug-related by the investigator through the end of the study.

Adverse Event tables will be presented for the following periods: Day 1 to Month 6 (treatment period) and Month 6 to Month 6 FU (follow-up period) as defined in section 4.2.12.

Adverse events starting more than 30 days after end of treatment will be considered as post-treatment AE.

Note: if an adverse event started after or at Month 6 visit date and if the subject entered the extension period, this adverse event will not be displayed for the main study, but only for the extension study.

For each of these 2 study periods, an overall summary table will be prepared presenting, by treatment group and overall, the number and percentage of subjects with

- any AE,
- any TEAE,

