6	Day 1	patient entered MAIN TREATMENT	remain ed in SCREEN ING (due to site error in diary completion)	Data regarding IMP intake will not be present for this period and data regarding menstrual periods will be present	n/a - missing in final DB	delete the answers to "is it your Menstrual period?" and start date questions, if any	n/a - remain in MAIN DB	First IMP intake in MAIN
---	-------	--------------------------------	---	--	---------------------------	---	-------------------------	--------------------------

Sponsor:	ObsEva		
Protocol:	18-OBE2109-002		
Document Version No.:	1.0	Document Date:	18-MAY-2021

Table 6 Mapping Rules for Signant Health Device

Cas e #	impacted visit	Patient status	Schedule of Signant Health daily diary	impact on data	Cytel action on IMP intake data	Cytel action on Menstrual data	Cytel mapping	cut off date (from eCRF)
1	Month 6	patient was included in EXT	remained in MAIN TREATMENT (due to Covid remote visit or to site error in diary completion)	data present in the Main datasets should be considered for the analysis of the extension study	mapping	n/a	from MAIN TREAT to EXT TREAT	First IMP intake in EXT
2	Month 6	patient was included in EXT	rescheduled to MAIN FU (due to site error in diary completion)	data present in the Main datasets should be considered for the analysis of the extension study	n/a - missing in final DB	n/a	from MAIN FU to EXT TREAT	First IMP intake in EXT
3	Month 6	patient entered MAIN FU	rescheduled to EXT TREATMENT (site error in	data present in the Extension datasets should be	delete answers to Yesterday IMP intake and to Today IMP intake if any	n/a	from EXT TREAT to MAIN FU	MONTH 6 visit date

Statistical Analysis Plan

Sponsor:	ObsEva		
Protocol:	18-OBE2109-002		
Document Version No.:	1.0	Document Date:	18-MAY-2021

			diary completion)	considered for the analysis of the Main study				
4	Month 6	patient entered MAIN FU	remained in MAIN TREATMENT (due to Covid remote visit or to site error in diary completion)	Data regarding IMP intake will be present for this period	delete answers to Yesterday IMP intake and to Today IMP intake if any	n/a	n/a - remain in MAIN DB	MONTH 6 visit date

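### The SAP's actual-treatment rule has no default for a subject with no active-drug days, so a placebo subject with sparse intake records can be tabulated as LGX 200 mg + ABT

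*SAP*

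**What the plan says.** SAP 3.1 defines the Safety Analysis Set as randomized subjects with at least one dose, and states: "Subjects will be analyzed according to treatment received". It then gives the derivation: "The actual treatment will be derived as follows, based on daily e-diary IMP intake data". What is counted, per treatment, is "The number of days with one pink tablet, one grey tablet and one red capsule taken".

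The steps are:

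- The Today entry is used first. If it is missing, the Yesterday entry of the next day stands in.
- If neither exists, "it will be assumed that no drug was taken on that day".
- The placebo label depends on one test: "If a subject received placebo with placebo ABT in more than 50% of days".
- A subject who fails that test goes to the active regimen with the larger number of days.
- Ties are settled as follows: "If the number of days is equal for two treatments groups containing active treatment then LGX 200 mg with ABT will be assigned".
- For a subject who discontinued, only data up to discontinuation count.

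The placebo test, the fall-through and the tie rule stand under a heading about treatment administration errors. The listing promised in SAP 3.1 covers only derived combinations that match none of the planned groups.

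SAP 7.1 (Appendix A, Table 5 case 6 and Table 6 cases 5 and 6) describes diaries left or set up in screening mode through site error, and says: "Data regarding IMP intake will not be present for this period". Those data are marked as absent from the final database.

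**The concern.** The placebo group is the only one with a minimum-days test, and failing it leads only to an active group. A woman who took placebo throughout but whose intake is poorly recorded fails the test, has zero days on 75 mg and zero on 200 mg + ABT, and is settled by the tie rule. She then counts as exposed to a regimen she never received. No step sends her back to her dispensed kit or randomized arm.

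Appendix A shows that the sponsor knows of intake records lost for reasons unrelated to whether drug was taken. So an absent record cannot safely be read as no drug.

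This matters because efficacy and PK are reduced to listings (SAP 4.6 and 4.7), which leaves the safety tables by treatment received as the main comparative output. Among subjects who took one regimen only, the error runs in one direction, into 200 mg + ABT, and would mix unexposed subjects into that column for adverse events, BMD and estradiol. The promised listing would not show them, because 200 mg + ABT is a planned group.

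**Working it through.** The plan gives no figure for this rule, so there is none to reproduce. The check applies the rule as written to subjects who took a single regimen.

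**Inputs**

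- Treatment period for a completer: Day 1 to the day before Month 6 (SAP 4.2.12). Month 6 is Day 169 (SAP Table 3), so 169 − 1 = 168 days.
- Placebo test: placebo days ÷ D > 0.5. SAP 3.1 does not define D.
- A day is covered if it has a Today entry or a Yesterday entry made the next day.

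**Two readings of D**

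(a) *All treatment days.* SAP 4.8.1.2 divides diary compliance by all days in the period. In addition, a missing day adds nothing to any regimen's count, so the no-drug assumption affects the placebo test only if such days are in D. The threshold is 0.5 × 168 = 84: 84/168 = 50.0% fails and 85/168 = 50.6% passes.

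(b) *Days with recorded intake.* A placebo-only subject with k ≥ 1 covered days has k/k = 100% and passes. With k = 0 there is nothing to divide, so the test is not met.

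| Regimen taken | Covered days of 168 | Reading (a) | Reading (b) |
|---|---|---|---|
| Placebo | 0 | 200 mg + ABT | 200 mg + ABT |
| Placebo | 1 to 84 | 200 mg + ABT | Placebo |
| Placebo | 85 to 168 | Placebo | Placebo |
| 75 mg | 0 | 200 mg + ABT | 200 mg + ABT |
| 75 mg | 1 to 168 | 75 mg | 75 mg |
| 200 mg + ABT | 0 to 168 | 200 mg + ABT | 200 mg + ABT |

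**Early stoppers.** Under (a) the threshold shrinks with time on treatment. For a subject who stops after 56 days it is 0.5 × 56 = 28, so 28 covered days give exactly 50% and fail.

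**Zero-record subjects.** One dose is enough for the Safety Set, and the Day 1 dose is taken at site and timed in the eCRF (Protocol 10.2.2.1). A subject can therefore belong to the set with no eDiary intake.

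**Effect of the Yesterday entry, reading (a), placebo, 168 days**

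- Alternate-day completion, 84 entries: all 168 days covered, so placebo.
- One gap at the start, then 84 entries: the first entry also covers the day before it, 84 + 1 = 85 days, so placebo. With 83 entries, 84 days are covered, so 200 mg + ABT.
- One gap at the end after 84 entries: no later entry fills it, so 84 days are covered and she goes to 200 mg + ABT.
- Entries made at random with probability p: expected coverage is 1 − (1 − p)². Simulating 4,000 subjects at each p gives:

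| p | Expected coverage | Assigned to 200 mg + ABT |
|---|---|---|
| 0.50 | 75% | 0% |
| 0.40 | 64% | 0.35% |
| 0.30 | 51% | about 43% |
| 0.25 | 44% | about 89% |
| 0.20 | 36% | over 99% |

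Scattered gaps are therefore largely repaired, while long blocks are not. A diary in screening mode produces a block, and with no intake question asked there is no Yesterday entry inside it.

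**The case against.** The best reply concerns scope. Tablets and capsules look alike across arms (Protocol 11.2 and 11.3), so a diary entry cannot identify the treatment and the count must already rest on kit identity. Read under its heading, the rule then settles only cases where a subject's kits differed, and a woman given only placebo kits has no error to settle. This may well be what was meant. But the lead-in introduces the derivation of actual treatment in general, no other assignment rule is given, and SAP 3.1 does not say how an error case is identified. A programmer following the text has only these steps.

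The second reply is that the denominator is undefined, and that on recorded days the problem shrinks to subjects with no covered days. That stands, and it limits the size of the point. It does not remove it, because those subjects still have no default.

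The third reply is that long gaps are unlikely. The protocol provides daily alarms, missed-entry alerts, remote checks (10.3.2) and a compliance check at each treatment visit after Day 1. For a completer, 84 uncovered days is three 28-day months, and Appendix A gives no duration for its cases. This stands as a comment on frequency.

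A reader might infer that any placebo subject who missed half her diary entries would be moved. The Yesterday entry rules that out: with exactly half the entries she may have every day covered.

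**Conclusion.** The rule as written can give a wrong treatment label, and SAP 3.1 contains nothing to stop it. On an all-days denominator, a placebo-only subject covered on half or fewer of her days (84 or fewer of 168 for a completer, fewer for an early stopper) is tabulated as LGX 200 mg + ABT. On a recorded-days denominator, only a subject with no covered days is, but that includes 75 mg as well as placebo subjects. Both results assume that the rule applies beyond confirmed administration errors, which the heading leaves open.

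The number affected cannot be found from the documents and may be zero. A reader might infer that the safety rates are shown to be distorted. They are not: SAP 1.2 says only that far fewer subjects were randomized than planned, and no diary coverage is reported. Nor can Phase 2b hot-flush rates size the effect, since Protocol 5.5.3 gives them for 200 mg without ABT and gives a placebo rate only at week 12.

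Two neighbouring choices may also look like errors. The majority rule can label as placebo a subject with under half her days on active drug, and the compliance fallback counts a missing day as not taken. Both are stated conventions, and the point does not rest on them.

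**What to change.** Amend SAP 3.1 before unblinding:

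1. Assign actual treatment from the dispensed kit numbers checked against the kit list. A subject dispensed only kits of her randomized arm keeps that arm.
2. Apply the days-based rule only to subjects with a confirmed dispensing error, which SAP 3.2 already records as a major deviation.
3. In that rule, define the 50% over days with recorded intake.
4. Apply the tie-break only when both active counts are above zero.
5. When intake data are absent, default to the dispensed kit.

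The cost is a few sentences and a simpler derivation. Kit numbers are issued through the IWRS and recorded at dispensing (Protocol 11.5 and 11.6), and dispensing is already to be listed (Listing 16.2.5.1), so no new data are needed.
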